4.4 Future Use of Samples

Following the completion of the trial, banked samples will be used for future correlative studies to evaluate the effects of different aerobic training prescriptions, relative to control, on blood-based biomarkers. Specific biomarkers of interest include metabolites and cytokine and angiogenic factors. A material transfer agreement (MTA) will be instituted before any samples are transferred.

Any projects outside of the scope of this protocol will need to be approved by the IRB/PB. A biospecimen correlative protocol detailing the proposed project will need to be approved by the IRB/PB prior to the start of the project.

5.0 THERAPEUTIC/DIAGNOSTIC AGENTS

There are no therapeutic agents in this trial.

6.1 CRITERIA FOR SUBJECT ELIGIBILITY

6.2 Subject Inclusion Criteria

- Aged 45–80 years
- Female
- Has been diagnosed with early-stage breast cancer
- Post-menopausal, defined as:
 - Age ≥ 45 with no menses for at least 2 years
 - Chemically induced menopause through ovarian suppression, as determined by the primary oncologist
- An interval of at least one year, but no more than five years, following the full completion of primary therapy for malignant disease. Primary therapy is defined as:
 - Surgery plus radiation
 - Surgery plus chemotherapy
 - Surgery plus trastuzumab
 - Surgery plus hormone therapy

Note: For patients who receive hormone therapy following surgery, the definition of one-year post-completion of therapy is defined by the surgery date. Patients who are currently receiving hormone therapy are eligible for enrollment.

- Weight of <205 kgs
- ECOG status of 0 or 1
- Life expectancy \geq 6 months
- Performing less than 150 minutes of structured moderate-intensity or strenuous intensity exercise per week.
- Exercise intolerance, defined by a VO_{2peak} below that predicted for active age- and sex-matched individuals (**see Appendix H**).
- Willing to be randomized to one of the study arms
- Able to complete an acceptable baseline CPET, in the absence of high risk ECG findings or other inappropriate response to exercise as determined by the investigator.
- Able to achieve an acceptable peak baseline CPET, as defined by any of the following criteria:
 - Achieving a plateau in oxygen consumption, concurrent with an increase in power output;
 - A respiratory exchange ratio \geq 1.10;
 - Attainment of maximal predicted heart rate (HR_{max}) (i.e., within 10 bpm of age-predicted HR_{max} [$HR_{max} = 220 - \text{Age}[\text{years}]$]);
 - Volitional exhaustion, as measured by a rating of perceived exertion (RPE) \geq 18 on the BORG scale (**see Appendix E**)

6.3 Subject Exclusion Criteria

- Any of the following absolute contraindications to cardiopulmonary exercise testing:
 - Acute myocardial infarction within 3–5 days of any planned study procedures
 - Unstable angina
 - Uncontrolled arrhythmia causing symptoms or hemodynamic compromise
 - Recurrent syncope
 - Active endocarditis
 - Acute myocarditis or pericarditis
 - Symptomatic severe aortic stenosis
 - Uncontrolled heart failure
 - Acute pulmonary embolus or pulmonary infarction within 3 months of any planned study procedures
 - Thrombosis of lower extremities
 - Suspected dissecting aneurysm
 - Uncontrolled asthma
 - Pulmonary edema
 - Respiratory failure
 - Acute non-cardiopulmonary disorders that may affect exercise performance or be aggravated by exercise (i.e., infection, renal failure, thyrotoxicosis)
- Presence of any other concurrent, actively treated malignancy
- History of any other malignancy treated within the past 3 years (other than non-melanoma skin cancer)

- Presence of metastatic disease
- Room air desaturation at rest $\leq 85\%$
- Mental impairment leading to inability to cooperate.
- Any other condition or intercurrent illness that, in the opinion of the investigator, makes the participant a poor candidate for the trial

7.1 RECRUITMENT PLAN

Potential participants will be identified by a member of the patient's treatment team, the protocol investigator, or members of the Exercise-Oncology Research Program (Ex-Onc) at Memorial Sloan Kettering Cancer Center (MSK). If the investigator is a member of the treatment team, s/he will screen their patients' medical records for suitable research study participants and discuss the study and their potential for enrolling in the research study. Potential participants contacted by their treating physician will be referred to the investigator/research staff of the study.

The principal investigator and Ex-Onc research staff may also screen the medical records of patients with whom they do not have a treatment relationship for the limited purpose of identifying patients who would be eligible to enroll in the study and to record appropriate contact information in order to approach these patients regarding the possibility of enrolling in the study.

During the initial conversation between the investigator/research staff and the patient, the patient may be asked to provide certain health information that is necessary to the recruitment and enrollment process. The investigator/research staff may also review portions of their medical records at MSK in order to further assess eligibility. They will use the information provided by the patient and/or medical record to confirm that the patient is eligible and to contact the patient regarding study enrollment. If the patient turns out to be ineligible for the research study, the research staff will destroy all information collected on the patient during the initial conversation and medical records review, except for any information that must be maintained for screening log purposes.

In most cases, the initial contact with the prospective participant will be conducted either by the treatment team, investigator, or the Ex-Onc research staff working in consultation with the treatment team. The recruitment process outlined presents no more than minimal risk to the privacy of the patients who are screened and minimal PHI will be maintained as part of a screening log. For these reasons, we seek a (partial) limited waiver of authorization for the purposes of (1) reviewing medical records to identify potential research subjects and obtain information relevant to the enrollment process; (2) conversing with patients regarding possible enrollment; (3) handling of PHI contained within those records and provided by the potential participants; and (4) maintaining information in a screening log of patients approached (if applicable).

Two strategies will be employed for participant recruitment:

1. Mail-Based Recruitment: Ex-Onc research staff will obtain from DataLine a list of potential participants meeting basic eligibility criteria.

Ex-Onc research staff will contact the potentially eligible patient's primary attending physician to confirm the patient's current status and to seek approval to send the patient a mail-based letter of introduction (**see Appendix B**) and a copy of the consent form. The letter of introduction will be signed by the protocol PI. Patients interested in trial participation will be directed to call the Ex-Onc office to ask any questions they may have, receive further instructions, and discuss next steps. To further assess eligibility of potentially eligible patients, the GLTEQ will be administered by phone. Patients meeting all study requirements will be scheduled for a baseline protocol appointment. Patients will have the opportunity to review the written consent form prior to completing any tests or procedures during the baseline protocol appointment. The patient will sign the consent form at this visit.

Patients not responding to the mailed letter of introduction within two weeks will be sent a second mailing. Patients still not responding a few weeks after the second mailing will be contacted by telephone by Ex-Onc personnel to gauge patient interest in trial participation. One additional phone call may be made to the patient, if needed. The study team will not make more than four total attempts (mailings and phone calls) to contact a patient.

2. Clinic-Based Recruitment: Potentially eligible patients attending a scheduled clinic visit with their primary attending oncologist at the Breast and Imaging Center (BAIC) will be approached at that visit. Patients may also be given a brochure at this visit with their oncologist as an introduction to the program. Ex-Onc research staff will obtain primary attending oncologist approval prior to or in conjunction with approaching any patient about trial participation. This initial encounter will include a discussion of the proposed trial, proposed treatments, and the rationale for use. Interested patients will answer questions from the GLTEQ to assess eligibility. Eligible patients interested in trial participation will have the opportunity to review and sign an informed consent during this clinic visit.

Following the initial consultation, interested participants will be contacted by telephone by Ex-Onc research staff to schedule the baseline assessment visit. Minorities and women are well-represented in the Breast Medicine clinics, and we anticipate appropriate representation in the trial accrual.

7.1 Blinding

This study is open label. Due to the nature of aerobic training interventions, participants, exercise physiologists, investigators and Ex-Onc research staff cannot be blinded to arm allocation.

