Resting left ventricular function by 3-dimensional echocardiography (3DE)	
Three-dimensional transthoracic echocardiograms will be performed by experienced sonographers and acquired with commercially available equipment (Vivid 7 or E9, GE Healthcare, Milwaukee, WI).
 
Following completion of the 2DE, a full volume dataset will be acquired using a matrix array transducer with gated 4 beat acquisitions for assessments of left ventricular (LV) volumes by 3DE. A 3DE acquisition of the entire LV will be generally performed in <10 seconds. All assessments will be stored digitally for offline analyses performed using EchoPAC PC workstation (version BT11, GE Medical, Milwaukee, WI).
 
Conventional 2D measurements of LV dimensions, Doppler, and diastolic function parameters will be performed and averaged over 3 cardiac cycles according to American Society of Echocardiography guidelines.²⁹⁻³¹
 
Left ventricular volumes and left ventricular ejection fraction (LVEF) by 3DE will be determined by manipulating the full volume dataset to derive conventional apical 4-, 3-, and 2-chamber views using TomTec offline analysis software (4D LV-Function, Unterschleisheim, Germany). After selection of reference points, a 3D endocardial contour will be automatically generated and manual adjustment will be performed as necessary. The resultant end-diastolic (EDV) and end-systolic volumes (ESV) will be used to calculate LVEF.³²

Symptom-limited CPET to assess peak oxygen consumption (VO_{2peak})	
VO_{2peak} will be evaluated using an electronic motorized treadmill test with 12-lead ECG monitoring (Mac® 5000, GE Healthcare) performed by certified exercise physiologists.
 
CPET provides assessment of peak oxygen consumption (VO_{2peak}). Expired gases will be analyzed continuously by a metabolic measurement system (Parvo Medics TrueOne 2400).
 
During the test, participants will begin walking on a treadmill at a participant-specific designated speed and grade for approximately 2 minutes. The speed and/or grade will then be increased every 1–2 minutes until exhaustion or a symptom-limitation is reached.
 
During exercise, oxyhemoglobin saturation will be monitored using finger pulse oximetry, while blood pressure will be measured manually by auscultatory sphygmomanometer every two minutes (± 1 minute).

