	The CPET may be terminated at the discretion of the exercise physiologist if abnormal ECG findings or abnormal response to exercise is observed, or if acceptable test criteria are not met.
Post VO_{2peak} left ventricular function by 2-dimensional echocardiography (2DE)	As soon as possible following completion of the CPET, participants will be placed in the supine position and 2DE grayscale images will be obtained in the apical 4-, 3-, and 2-chamber views. Wall motion scoring index (WMSI) will be calculated at rest and post-exercise using the 17 segment model by adding the individual segment scores (1 = normal; 2 = hypokinesia; 3 = akinesia; 4 = dyskinesia) and dividing by number of segments scored. ²⁹ 2D LV volumes and LVEF will be calculated offline using the modified Simpson's biplane method. Cardiac output will be calculated as the product of LV stroke volume and heart rate, indexed to body surface area (BSA).
Pulmonary function testing	Pulmonary function will be determined using standard spirometry. All measures will be performed in a sitting position according to the American Thoracic Society guidelines. ³⁶
Regional arterial stiffness	
Conduit regional artery stiffness of the entire aorta will be assessed non-invasively by measuring carotid-femoral pulse wave velocity (PWV) using 2 hand-held tonometers (SPT-301 Millar Instruments, Houston, TX).
 
Carotid and femoral artery waveforms will be recorded simultaneously with the mechanotransducers directly applied to the skin over the greatest area of pulsation. Twenty consecutive reproducible beats will be collected simultaneously at both sites, with a concurrent electrocardiograph to obtain R-R intervals.
 
Pulse transit time will be determined as the difference in time from R interval to systolic upstroke at each location. Systolic upstroke will be determined by identifying the foot or —notch of the blood pressure waveform. This will be done by applying a band pass filter between 5-30 Hz, selecting the minimum value of the filtered signal.
 
Pulse distance will be determined using anthropometric measuring tape subtracting the distance from carotid measurement to sternal notch from the distance from sternal notch to femoral pulse measurement. This method has been shown to be the optimal non-invasive measurement compared to invasive measure. PWV will then be determined by taking the pulse transit time/distance.

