Flow-mediated dilatation (FMD) to assess endothelial function	
Peripheral artery flow-mediated dilatation (FMD) will be performed on one arm with the subject in a supine position with the forearm extended and slightly supinated.
 
A rapid inflator blood pressure cuff will be placed on the forearm just distal to the antecubital crease and the brachial artery will be imaged using high-resolution B-mode ultrasound and a 7.5MHz linear array transducer (Terason, t3200). Ten-second r-wave triggered digital clips (artery diastole) will be captured at baseline (following 10min of supine rest), during five minutes of forearm occlusion, and a 120 sec r-wave triggered digital clip will

	
be captured beginning at cuff deflation (hyperemia) as previously described.³⁷
 
Offline analysis using specialized software (Brachial Tools, Medical Imaging Applications, Illinois) will permit for identification of peak dilation and dilation at specific pre-specified time points (60, 120 sec).³⁷

Dual energy x-ray absorptiometry (DEXA) to assess body composition	
Body fat percentage, and lean and fat body mass will be assessed by dual energy x-ray absorptiometry using a Lunar Prodigy multiple detector fan-beam densitometer (GE Medical Systems, Madison, WI). After calibration with an anthropomorphic phantom, single-beam, whole-body scanning will be employed on supine-positioned subjects. Data will be obtained from each scan for fat and lean body mass expressed to the nearest tenth of a gram (and percent) for the total body region, as well as in defined body zones (e.g., legs, trunk and arms).
 
In the two hours prior to the DEXA scan, participants will be asked to avoid a large meal, avoid caffeine, avoid alcohol, and avoid tobacco. Participants will also be instructed to avoid strenuous activity for at least twelve hours before the scan.
 
Efforts will be made for baseline and follow up DEXA assessments to be performed on the same machine.

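### Stored echocardiography and FMD files could be read without arm or visit labels, but the plan provides for no masked reading

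*Combined protocol and SAP*

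**What the plan says.** Section 7.1 is the only text on blinding. It declares the study open label and states that "participants, exercise physiologists, investigators and Ex-Onc research staff cannot be blinded to arm allocation". The reason given is "Due to the nature of aerobic training interventions".

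Table 1 in Section 8.2 describes how the imaging measures are obtained and read:

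- **Resting 3D echocardiography.** "Three-dimensional transthoracic echocardiograms will be performed by experienced sonographers". Reading is a later step: "All assessments will be stored digitally for offline analyses performed using EchoPAC PC workstation". For LV volumes and LVEF, "a 3D endocardial contour will be automatically generated and manual adjustment will be performed as necessary".
- **Post-exercise 2D echocardiography.** "Wall motion scoring index (WMSI) will be calculated at rest and post-exercise using the 17 segment model by adding the individual segment scores", each segment receiving a score from 1 to 4. The 2D volumes and LVEF are also calculated offline.
- **FMD.** Digital clips are captured, then processed by "Offline analysis using specialized software", which identifies peak dilation. No manual step is described.

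Section 12.2 lists resting LV function by 3D echocardiography, post-exercise LVEF and FMD among the secondary end points. Table 2 schedules these measures at baseline and at the Week 17 follow-up. Section 8.2 places randomization after the baseline assessments.

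**The concern.** The reason in Section 7.1 explains why a participant or an exercise physiologist must know the arm. It does not explain why someone tracing a stored ventricle at a workstation must know it. Acquisition and reading are already separate steps in Table 1, so masking the reading would not change visits, testing or training. Yet the supplied text contains no masked reading, no removal of arm or visit labels, no core laboratory and no assignment of readers.

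The Week 17 images are acquired after allocation. A reader who knows that a file is a follow-up scan from a training arm may, without intending to, adjust a contour or score a segment in the expected direction. The regression models and multiple imputation in Section 14.3.2 take the readings as given and cannot remove such a shift. At stake are the between-arm comparisons of cardiac function and, with less documented room for judgement, endothelial function.

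**Working it through.** The plan states no figure on this point, so there is none to reproduce. The check has two parts.

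**1. Does the stated reason reach the reading step?**

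| Step | Who, according to the plan | Does the Section 7.1 reason apply? |
|---|---|---|
| Training and stretching sessions | Exercise physiologists | Yes |
| CPET (primary end point) | Exercise physiologists, measured live | They are named as unblinded, and there is no stored reading to mask |
| Echocardiogram acquisition | Sonographers, not named in Section 7.1 | Unspecified |
| Offline echocardiogram reading, with manual contour adjustment and segment scores | Not identified | No |
| Offline FMD analysis by software | Not identified | No |

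**2. How much could a reading shift matter?** This is an illustration, not an estimate.

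Inputs from the documents:
- 58 evaluable participants per group (Section 14.2).
- 115 of 174 participants randomized at the first site, with 59 to come (Section 1.0).

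Assumptions not in the documents:
- A two-sided 5% level. Section 14.2 gives 0.025 for the two primary pairwise comparisons, and Section 14.3.2 gives no level for secondary end points.
- No true effect.
- A systematic shift of 0.5 or 1 standard error (SE) in one arm relative to the other.

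SE of an arm difference, in SD units of the measure: sqrt(2/58) = 0.186. The two shifts are therefore 0.5 × 0.186 = 0.09 SD and 1 × 0.186 = 0.19 SD.

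False-positive rate with a shift of k standard errors: P(|Z + k| > 1.96).
- k = 0.5: P(Z > 1.46) + P(Z < −2.46) = 0.072 + 0.007 = 0.079.
- k = 1: P(Z > 0.96) + P(Z < −2.96) = 0.1685 + 0.0015 = 0.170.

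A noncentral t calculation on a slightly different grid agrees: 8.3% at 0.1 SD and 18.7% at 0.2 SD.

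**Masking only the participants still to come.** Suppose that every first-site image has already been read unmasked, which the documents do not say. The share of the shift that remains is 115/174 = 0.66. By arm the share is nearly the same: 38/58 = 0.66 in Arms A and C, and 39/58 = 0.67 in Arm B.
- k = 0.66 × 0.5 = 0.33: P(Z > 1.63) + P(Z < −2.29) = 0.052 + 0.011 = 0.063.
- k = 0.66 × 1 = 0.66: P(Z > 1.30) + P(Z < −2.62) = 0.097 + 0.004 = 0.101.

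| Assumed shift | No masking | Only the remaining 59 masked |
|---|---|---|
| 0.5 SE (0.09 SD) | about 8% | about 6% |
| 1 SE (0.19 SD) | about 17% | about 10% |

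**The case against.** The strongest reply is that Section 7.1 does not say readers are unmasked. It names four groups. Sonographers, offline readers and the trial statisticians are not among them, and no section says who reads the files. A reader might infer that the plan declares every member of staff unblindable. It does not: masking of the readers is unspecified rather than ruled out. This stands, but it does not close the gap, because nothing in the plan requires masking.

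Other parts of the reply also stand:

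- **Room for judgement is uneven.** It would be tempting to say that FMD, too, rests on a reader's hand. Table 1 describes only software for FMD. The documented manual adjustment of a listed end point is the 3D contour, and only as needed. Segment scoring is described, but the wall motion index is not itself listed in Section 12.2.
- **The contrast matters.** A reader who favours training-arm scans would shift Arms A and B alike, so the effect would largely cancel between them. The illustrative rates apply mainly to comparisons with Arm C.
- **The fix may be partial.** About two thirds of participants were randomized before the move. Whether their images have been read, or can still be retrieved, is not stated.
- **The outcomes are secondary** in a trial that Section 16.2 calls phase II, and the sample size does not rest on them.

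These points limit the size of the concern. None gives a reason to leave stored files unmasked.

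**Conclusion.** The concern holds in a limited form. The plan provides no masked outcome reading, and its reason for not blinding does not reach the offline analysis of echocardiography and FMD. Week 17 readings of these secondary end points are open to reader bias, chiefly in comparisons of a training arm with Arm C. The evidence is stronger for echocardiography than for FMD.

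The rates of 8% to 17%, and 6% to 10% with partial masking, depend on the assumed shift and the assumed 5% level. They show that a small systematic shift would matter. They do not show that one has occurred or will occur, and the documents support no estimate of its size.

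A reader might also infer that the primary result is in doubt on this ground. The documents do not support that: VO2peak is measured live by CPET, and offline reading plays no part in it. For the same reason, masked image reading would do nothing for the fact that unblinded staff conduct that test. The change is worth making because it is cheap and because this bias cannot be repaired in the analysis; it is not a condition for the primary analysis.

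**What to change.** - In Section 7.1, confine the statement on blinding to participants and to those who deliver the sessions and tests.
- In Section 7.1 and Table 1, say who reads the echocardiography and FMD files. Require that the files be given a study code, stripped of arm and visit labels, and read in mixed order by whoever already reads them. Require that the readings be locked before the code is broken.
- State how the first-site images were read, and mask any that have not yet been read.

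The cost is a file-coding step before reading, reading in batches, and a few sentences of text. Visits and tests do not change. The main drawback is that if first-site images (115 of 174 participants) were already read unmasked, reading conditions would differ by site. The report should then say so.
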